9.1 Appendix 1 – Adverse Events

9.1.1 Definitions

AE – Averse Event - Any untoward medical occurrence, unintended disease or injury, or untoward clinical signs (including abnormal laboratory findings) in subjects, users or other persons, whether or not related to the investigational medical device.

SAE – Serious Adverse Event - Event that leads to death, to a life-threatening illness or injury, or a permanent impairment of a body structure or a body function, or in-patient or prolonged hospitalization, or medical or surgical intervention to prevent life-threatening illness or injury or permanent impairment to a body structure or a body function, foetal distress, death or a congenital abnormality.

ADE – Adverse Device Effect - Includes adverse events resulting from insufficient or inadequate instructions for use, deployment, implantation, installation, or operation, or any malfunction of the investigational medical device or use errors and intentional misuse.

Device deficiency is an inadequacy of a medical device with respect to its identity, quality, durability, reliability, safety or performance. A device deficiency should be reported as AE or SAE according to the AE and SAE definitions.

SADE – Serious Adverse Device Effect - Adverse device effect that has resulted in any of the consequences characteristic of a serious adverse event.

[figure not shown]
ASADE – Anticipated Serious Device Effect - An effect which by its nature, incidence, severity or outcome has been identified in the current version of the risk analysis report.

[figure not shown]
[figure not shown]
USADE – Unanticipated Serious Device Effect - An effect which by its nature, incidence, severity or outcome has not been identified in the current version of the risk analysis report.

[figure not shown]
[figure not shown]

The Cardioband logo is written in a stylized, cursive font.	REPAIR - Transcatheter REPAIR of Mitral Insufficiency with Cardioband System Post Market Study Protocol ID CB1-3	A solid black rectangular redaction box.
---	---	--

[figure not shown]

[figure not shown]
	
REPAIR - TranscatheteR REPair of Mitral Insufficiency with CaRdioband System Post Market Study Protocol ID CB1-3
	
---	---	---

Cardioband

REPAIR - Transcatheter REPair of Mitral Insufficiency
with CaRdioband System
Post Market Study
Protocol ID CB1-3

	
REPAIR - Transcatheter REPair of Mitral Insufficiency with CaRdioband System Post Market Study Protocol ID CB1-3
	
---	---	---

	
REPAIR - Transcatheter REPAIR of Mitral Insufficiency with CaRdioband System Post Market Study Protocol ID CB1-3
	
---	---	---

9.2 Appendix 2 – Reportable Events - by MVARC

The following is a list of events defined by MVARC as clinical endpoints to be collected in all trials of mitral valve therapies. The different events should be reviewed and reported in light of the following definitions.

[figure not shown]

Mortality
	
 1. Cardiovascular vs. non-cardiovascular mortality 
 a. Cardiovascular mortality - Any of the following contributing conditions: 
 • Heart failure (subclassified into left ventricular vs. right ventricular dysfunction) • Myocardial infarction • Major bleeding • Thromboembolism • Stroke • Arrhythmia and conduction system disturbance • Cardiovascular infection and sepsis (e.g., mediastinitis and endocarditis) • Tamponade • Sudden, unexpected death • Other cardiovascular • Device failure • Death of unknown cause (adjudicated as cardiovascular) b. Non-cardiovascular mortality - Any death in which the primary cause of death is clearly related to another condition: 
 • Non-cardiovascular infection and sepsis (e.g., pneumonia) • Renal failure • Liver failure • Cancer • Trauma • Homicide • Suicide • Other non-cardiovascular 2. Periprocedural vs. non-periprocedural mortality: 
Death is considered periprocedural if occurring within 30 days of the intervention or beyond 30 days in the patient not yet discharged


Hospitalization
	
Hospitalization is defined as admission to an inpatient unit or ward in the hospital for ≥ 24 h, including an emergency department stay.
 
Hospitalizations planned for pre-existing conditions are excluded unless there is worsening of the baseline condition.
 
Hospitalization is Further Sub-classified as:
 
 1. Heart failure hospitalization: Both of the following additional criteria are present: 
 • Symptoms, signs and/or laboratory evidence of worsening heart failure • Administration of intravenous or mechanical heart failure therapies • Patients hospitalized with heart failure are further subclassified as: 
 ○ Primary (cardiac related) heart failure hospitalization ○ Secondary (non-cardiac related) heart failure hospitalization 2. Other cardiovascular hospitalization: such as for coronary artery disease, acute myocardial infarction, hypertension, cardiac arrhythmias, cardiomegaly, pericardial effusion, atherosclerosis, stroke, or peripheral vascular disease without qualifying heart

	REPAIR - Transcatheter REPAIR of Mitral Insufficiency with Cardioband System Post Market Study Protocol ID CB1-3	
---	---	---

	
failure
 
3. Non-cardiovascular hospitalization: not due to heart failure or other cardiovascular causes, as defined above

Neurologic events	
Stroke and transient ischemic attack Diagnostic criteria:
 
 Acute episode of a focal or global neurological deficit with at least 1 of the following: 
 Change in the level of consciousness Hemiplegia, hemiparesis, numbness, or sensory loss affecting 1 side of the body Dysphasia or aphasia, hemianopia, amaurosis fugax, or other neurological signs or symptoms consistent with stroke In addition, there is no other readily identifiable non-stroke cause for the clinical presentation (e.g., brain tumour, trauma, infection, hypoglycaemia, peripheral lesion, pharmacological influences) as determined by or in conjunction with the designated neurologist 
The neurological event type classification
 
 Stroke: duration of a focal or global neurological deficit ≥ 24 h OR ,24 h if available neuroimaging documents a new intracranial or subarachnoid haemorrhage (haemorrhagic stroke) or central nervous system infarction (ischaemic stroke) OR the neurological deficit results in death TIA: duration of a focal or global neurological deficit ,24 h and neuroimaging does not demonstrate a new haemorrhage or infarct 
Confirmation of the diagnosis of stroke or TIA requires at least 1 of the following:
 
 Neurologist or neurosurgical specialist, or Neuroimaging procedure (CT scan or brain MRI) 
Stroke/TIA timing classification
 
 Periprocedural if it occurs within 30 days of the intervention, or if beyond 30 days in the patient not yet discharged. A periprocedural stroke/TIA may be further considered immediate if it occurs within 24 h of the procedure or within 24 h of awakening from general anaesthesia if beyond 24 h. Nonperiprocedural if it occurs beyond 30 days after the intervention and after the patient has been discharged. 
Stroke/TIA aetiology classification
 
 Ischaemic: an acute episode of focal cerebral, spinal, or retinal dysfunction caused by infarction of the central nervous system tissue Haemorrhagic: an acute episode of focal or global cerebral or spinal dysfunction caused by intraparenchymal, intraventricular, or subarachnoid haemorrhage Undetermined: if there is insufficient information to allow categorization as ischaemic or haemorrhagic 
Stroke severity is further classified as
 
 Disabling stroke: an mRS score ≥ 2 at 90 days plus an increase in ≥ 1 mRS category from the pre-stroke baseline Non-disabling stroke: an mRS score ,2 at 90 days or without an increase ≥ 1 mRS category from the pre-stroke baseline
Myocardial infarction	
Definition of MI after transcatheter and surgical mitral valve replacement:
 
 Periprocedural MI (≤ 48 h after the index procedure) 
 In patients with normal baseline CK-MB (or cTn): The peak CK-MB measured within 48 h of the procedure rises to ≥ 10x the local laboratory ULN plus new ST-segment elevation or depression of ≥ 1 mm in ≥ 2 contiguous leads (measured 80 ms after the J-point), or to ≥ 5x ULN with new pathological Q waves in ≥ 2 contiguous leads or new persistent LBBB, OR in the absence of CK-MB measurements and a normal baseline cTn, a cTn (I or T) level measured within 48 h of the PCI rises to ≥ 70x the local laboratory ULN plus new ST-segment elevation or depression of ≥ 1 mm in ≥ 2

	REPAIR - Transcatheter REPAIR of Mitral Insufficiency with CaRdioband System Post Market Study Protocol ID CB1-3	
---	---	---

	
contiguous leads (measured 80 ms after the J-point), or $\geq 35 \times$ ULN with new pathological Q waves in ≥ 2 contiguous leads or new persistent LBBB.
 
 In patients with elevated baseline CK-MB (or cTn): The CK-MB (or cTn) rises by an absolute increment equal to those levels recommended above from the most recent pre-procedure level plus, new ECG changes as described. 
2. Spontaneous MI (.48 h after the index procedure) - Detection of rise and/or fall of cardiac biomarkers (preferably cTn) with at least 1 value above the 99th percentile URL (or ULN in the absence of URL) together with at least 1 of the following:
 
 Symptoms of ischaemia ECG changes indicative of new ischaemia (new ST-segment or T-wave changes or new LBBB) or new pathological Q waves in ≥ 2 contiguous leads Imaging evidence of a new loss of viable myocardium or new wall motion abnormality 
3. MI associated with sudden, unexpected cardiac death: Sudden cardiac death or cardiac arrest, often with symptoms suggestive of myocardial by presumably new ST-segment elevation or new LBBB and/or evidence of fresh thrombus by coronary angiography and/or at autopsy, but death occurs before blood samples could be obtained or at a time before the appearance of cardiac biomarkers in ischaemia, and accompanied the blood.
 
4. Pathological findings of an acute myocardial infarction

--	--

Access and vascular complications	
Vascular complications:
 
 Major access site vascular complications, including: 
 Aortic dissection or aortic rupture, or Access site-related arterial or venous injury (dissection, stenosis, ischaemia, arterial, or venous thrombosis including pulmonary emboli, perforation, rupture, arteriovenous fistula, pseudoaneurysm, haematoma, retroperitoneal haematoma, atrial septal defect), irreversible nerve injury, or compartment syndrome resulting in death; hemodynamic compromise; life-threatening, extensive, or major bleeding (MVARC bleeding scale); visceral ischaemia; or neurological impairment, or Distal embolization (non-cerebral) from a vascular source requiring surgery or resulting in amputation or irreversible end-organ damage, or Unplanned endovascular or surgical interventions resulting in death; life-threatening, extensive, or major bleeding (MVARC bleeding scale); visceral ischaemia; or neurological impairment Minor access site vascular complications, including: 
 Access site arterial or venous injury (dissection, stenosis, arterial, or venous thrombosis including pulmonary emboli, ischaemia, perforation, rupture, arteriovenous fistula, pseudoaneurysm, haematoma, retroperitoneal haematoma, atrial septal defect) not resulting in death; life-threatening, extensive, or major bleeding (MVARC scale); visceral ischaemia; or neurological impairment, or Distal embolization treated with embolectomy and/or thrombectomy not resulting in amputation or irreversible end-organ damage, or Any unplanned endovascular stenting or unplanned surgical intervention not meeting the criteria for a major vascular complication, or Vascular repair (via surgery, ultrasound-guided compression, transcatheter embolization, or stent-graft) 
Cardiac structural complications due to access-related issues
 
 Major cardiac structural complications, including: 
 Cardiac perforation* or pseudoaneurysm resulting in death, life-threatening bleeding, hemodynamic compromise, or tamponade, or requiring unplanned
--	---

	REPAIR - Transcatheter REPAIR of Mitral Insufficiency with Carotoband System Post Market Study Protocol ID CB1-3	
---	---	---

	
surgical or percutaneous intervention
 
2. Minor cardiac structural complications, including:
 
 • Cardiac perforation* or pseudoaneurysm not meeting major criteria 
*Including the left ventricle, left atrium, coronary sinus, right atrium, and right ventricle. †May arise from the access procedure per se or complications from vascular closure devices.
 
‡Meeting pre-specified criteria for a hemodynamically significant shunt, or requiring unplanned percutaneous or surgical closure.

Bleeding complications	
MVARC Primary Bleeding Scale*
 
 1. Minor Any overt, † actionable sign of haemorrhage (e.g., more bleeding than would be expected for a clinical circumstance, including bleeding found by imaging alone) that meets ≥ 1 of the following: requiring nonsurgical medical intervention by a health care professional; leading to hospitalization or increased level of care; prompting evaluation; or requires 1 or 2 U of whole blood or packed RBC transfusion and otherwise does not meet criteria for major, extensive, or life-threatening bleeding. 2. Major Overt bleeding either associated with a drop in the haemoglobin of ≥ 3.0 g/dl‡ or requiring transfusion of ≥ 3 U of whole blood or packed RBCs AND does not meet criteria of life-threatening or extensive bleeding. 3. Extensive Overt source of bleeding with drop in haemoglobin of ≥ 4 g/dl‡ or whole blood or packed RBC transfusion ≥ 4 U within any 24-h period, or bleeding with drop in haemoglobin of ≥ 6 g/dl‡ or whole blood or packed RBC transfusion ≥ 4 U (BARC type 3b) within 30 days of the procedure. 4. Life-threatening Bleeding in a critical organ, such as intracranial, intraspinal, intraocular, or pericardial necessitating surgery or intervention, or intramuscular with compartment syndrome OR bleeding causing hypovolemic shock or hypotension (systolic blood pressure < 90 mm Hg lasting > 30 min and not responding to volume resuscitation) or requiring significant doses of vasopressors or surgery. 5. Fatal Bleeding adjudicated as being a proximate cause of death. Severe bleeding adjudicated as being a major contributing cause of a subsequent fatal complication, such as MI or cardiac arrest, is also considered fatal bleeding. 
*Modified with permission from VARC-2.5 †"Overt" bleeding is defined by any of the following criteria being met: Reoperation after closure of sternotomy for the purpose of controlling bleeding; chest tube output > 2 l within any 24-h period, > 350 ml within the first post-operative hour, ≥ 250 ml within the second post-operative hour, or 150 ml within the third post-operative hour; or visible bleeding from the vascular system either at or remote from the access/surgical site. ‡Adjusted for the number of units of blood transfused (1 U packed red blood cells or whole blood is equivalent to 1 g/dl haemoglobin). §Modified from BARC.6 BARC, bleeding academic research consortium; IV, intravenous; MVARC, Mitral Valve Academic Research Consortium; RBC, red blood cells; VARC, valve academic research consortium.

Acute kidney injury	
Definition and stages of acute kidney injury:
 
Maximal change in sCr from baseline to 7 days post-procedure
 
Stages
 
 • Stage 1 Increase in sCr to 150%–199% (1.50–1.99x increase vs. baseline), increase of ≥ 0.3 mg/dl (≥ 26.4 mmol/l) within 48 h, or urine output < 0.5 ml/kg/h for ≥ 6 h but < 12 h • Stage 2 Increase in sCr to 200%–299% (2.00–2.99x increase vs. baseline) or urine output < 0.5 ml/kg/h for ≥ 12 h but < 24 h • Stage 3 Increase in sCr to $\geq 300\%$ (3.0x increase vs. baseline), sCr of ≥ 4.0 mg/dl,

	REPAIR - Transcatheter REPAIR of Mitral Insufficiency with CaRdioband System Post Market Study Protocol ID CB1-3	
---	---	---

	
(≥ 354 mmol/l) with an acute increase of ≥ 0.5 mg/dl (44 mmol/l), urine output ,0.3 ml/kg/h for ≥ 24 h, or anuria for ≥ 12 h; patients receiving renal replacement therapy are considered stage 3 irrespective of other criteria

Arrhythmias and conduction system disturbances	
Arrhythmias and conduction system disturbances
 
 1. Procedure-related new or worsened cardiac conduction disturbance (including first-, second- [Mobitz I or Mobitz II], or third-degree AV block; incomplete and complete right bundle branch block; intraventricular conduction delay; left bundle branch block; left anterior fascicular block; or left posterior fascicular block, including heart block) requiring a permanent pacemaker implant; each subclassified as persistent or transient 2. New-onset atrial fibrillation (or flutter)† 3. New-onset ventricular tachycardia or fibrillation 4. Pacemaker or defibrillator lead dislodgement 
Arrhythmias and conduction system disturbances are subclassified according to:
 
 1. The occurrence of hemodynamic instability 2. Need for therapy including electrical/pharmacological cardioversion or initiation of a new medication (oral anticoagulation, rhythm, or rate control therapy) 3. Need for new permanent pacemaker and/or defibrillator implantation, including the indication(s) and the number of days post-implant. For patients with defibrillators, the number of appropriate and inappropriate shocks should be recorded. 
*The type of permanent pacemaker should be recorded (e.g., single vs. dual chamber, biventricular). †Which lasts sufficiently long to be recorded on a 12-lead electrocardiogram, or at least 30 s on a rhythm strip. AV, atrioventricular.

Specific device-related technical failure issues and complications	
Technical failure (measured at exit from the catheterization laboratory):
 
 1. Procedural mortality; 2. Failure in access, delivery, or retrieval of the device delivery system; 3. Failure in deployment and correct positioning of the first intended device; 4. Emergency surgery or reintervention related to the device or access procedure. 
Device failure (measured at 30 days and at all later post-procedural intervals)
 
 1. procedural mortality or stroke; or 2. failure in placement and positioning of the device; or 3. unplanned surgical or interventional procedures related to the device or access procedure; or 4. lack of safety and performance of the device, including: 
 • evidence of structural or functional failure • device-related technical failure issues and complications • significant mitral stenosis 
Procedural Failure (measured at 30 days)
 
 1. Device failure 2. major device or procedure related serious adverse events, including: 
 • Death • Stroke • Life-threatening bleeding (MVARC scale) • Major vascular complications • Major cardiac structural complications • Stage 2 or 3 acute kidney injury (includes new dialysis) • Myocardial infarction or coronary ischaemia requiring PCI or CABG • Severe hypotension, heart failure, or respiratory failure requiring intravenous pressors or invasive or mechanical heart failure treatments such as ultrafiltration or hemodynamic assist devices, including intra-aortic balloon pumps or left ventricular or biventricular assist devices, or prolonged intubation for ≥ 48 h. • Any valve-related dysfunction, migration, thrombosis, or other complication requiring surgery or repeat intervention

	
REPAIR - Transcatheter REPAIR of Mitral Insufficiency with CaRdioband System Post Market Study Protocol ID CB1-3
	
---	--	---

	
Patient failure (measured at 1 year)
 
 1. Device failure 2. Patient returned to the pre-procedural setting 3. rehospitalizations or reinterventions for the underlying condition (e.g., mitral regurgitation, heart failure); 4. No Improvement from baseline in symptoms (e.g., no NYHA improvement by ≥ 1 functional class); and 5. No Improvement from baseline in functional status (e.g., 6-min walk test did not improve by ≥ 50 m); and 6. No Improvement from baseline in quality-of-life (e.g., no improvement in Kansas City Cardiomyopathy Questionnaire by at least ≥ 10) 
*MR reduction is considered optimal when post-procedure MR is reduced to trace or absent. MR reduction is considered acceptable when post-procedure MR is reduced by at least 1 class or grade from baseline and to no more than moderate (2+) in severity. For clinical trials and registry studies, assessment of baseline and post-procedure MR must be made by an echocardiographic core laboratory. For large observational databases, baseline and post-procedure MR may be assessed by physicians trained in echocardiography evaluation.

--	---

Mortality, Hospitalization, Neurological events and Myocardial Infarction are events which should be adjudicated by an independent central adjudication committee.

For further details for each event, please refer to The Mitral Valve Academic Research Consortium (MVARC) Guidelines: Clinical Trial Design Principles and Endpoint Definitions for Transcatheter Mitral Valve Repair and Replacement (JACC 2015;66(3):278-307).

- Document End -

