	
 • Discharged from index hospitalization • NYHA class improvement by at least 1 level from baseline 
9) Days alive and out of hospital (due to major cardiovascular events) at 1 year
 
10) Freedom from all-cause mortality and major adverse events defined as disabling stroke, myocardial infarction (peri-procedural or spontaneous), renal failure requiring dialysis, life-threatening bleeding, cardiac tamponade and device related cardiac surgical intervention at 30 days from the implant procedure or hospital discharge, whichever is later. (Individual components will also be evaluated).
 
11) Need for urgent/emergent surgical intervention

Sample Size Considerations	
Based on the results of the Cardioband CE mark study (Protocol ID CB 1-2), the present study with a sample size of 50 subjects will have greater than 80% power to detect a reduction in MR severity of at least one grade (CE mark study showed improvement in MR severity of at least one grade in >80% of subjects in CE mark study).
 
Based on the results of the Cardioband CE mark study (Protocol ID CB 1-2), the present study with a sample size of 50 subjects will have greater than 90% power to detect an improvement of 75 m in 6 minute walk test at 6 months (CE Mark study showed an improvement of 93.3 m ± 90.3 m).

Inclusion Criteria	
 1) Age ≥18 years 2) Severe (3+ to 4+) secondary Mitral Regurgitation 3) Symptomatic heart failure (NYHA Class III-IVa) despite guideline directed medical therapy including CRT if indicated 4) The Local Site Heart Team concur that surgery will not be offered as a treatment option and that medical therapy is the intended therapy. 5) Transfemoral access and transseptal deployment of the Cardioband is determined to be feasible 6) Subject is willing and able to provide informed consent and follow protocol
Exclusion Criteria	
 1) EF < 20% 2) LVEDD ≥ 70 mm 3) Heavily calcified annulus or leaflets 4) Significant CAD requiring revascularization 5) Active bacterial endocarditis 6) Any percutaneous coronary, carotid, endovascular intervention or carotid surgery within 30 days or any coronary or endovascular surgery within 3 months 7) Renal insufficiency requiring dialysis

	REPAIR - Transcatheter REPAIR of Mitral Insufficiency with CaRdioband System Post Market Study Protocol ID CB1-3	
---	---	---

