3.2. Study Endpoints

3.2.1. Primary Endpoint (powered):

- Reduction in severity of MR at 30 days of at least one category on a 0-4 scale.

3.2.2. Key Secondary Endpoint (powered):

- Change in 6 minute walk test at 6 months

3.2.3. Secondary Endpoints (all at 6, 12, and 24 months except as indicated) :

- Key Secondary Endpoint (powered): Change in 6 minute walk test at 6 months.
- Secondary Endpoints (all at 6, 12, and 24 months except as indicated) :
 - 1) MR severity
 - 2) 6 minute walk distance
 - 3) Quality of life as assessed by the Kansas City Cardiomyopathy Questionnaire (KCCQ) (also at 30 days)
 - 4) NYHA Class (also at 30 days)
 - 5) Left Ventricular End Diastolic Volume (LVEDV)
 - 6) Left Ventricular End Systolic Volume (LVESV)
 - 7) Device success defined as deployment of the Cardioband, with MR reduction at hospital discharge.
 - 8) Individual patient success (6 months and 1 year) defined as device success and the following:
 - 9) Discharged from index hospitalization
 - 10) NYHA class improvement by at least 1 level from baseline
 - 11) Days alive and out of hospital (due to major cardiovascular events) at 1 year
 - 12) Freedom from all-cause mortality and major adverse events defined as disabling stroke, myocardial infarction (peri-procedural or spontaneous), renal failure requiring dialysis, life-threatening bleeding, cardiac tamponade, and device related cardiac surgical intervention

	REPAIR - Transcatheter REPAIR of Mitral Insufficiency with CaRdioband System Post Market Study Protocol ID CB1-3	
---	---	---

at 30 days from the implant procedure or hospital discharge, whichever is later. (Individual components will also be evaluated).

- 13) Need for urgent/emergent surgical intervention

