3.3. Inclusion/Exclusion

[figure not shown]
[figure not shown]
The Principal Investigator will determine the patient's suitability for Cardioband implantation, based on the following inclusion/exclusion criteria:

3.3.1. Inclusion Criteria:

- 1) Age ≥ 18 years
- 2) Severe (3+ to 4+) secondary Mitral Regurgitation
- 3) Symptomatic heart failure (NYHA Class III-IVa) despite guideline directed medical therapy including CRT if indicated
- 4) The Local Site Heart Team concur that surgery will not be offered as a treatment option and that medical therapy is the intended therapy.
- 5) Transfemoral access and transeptal deployment of the Cardioband is determined to be feasible
- 6) Subject is willing and able to provide informed consent and follow protocol

3.3.2. Exclusion Criteria:

- 1) EF < 20%
- 2) LVEDD ≥ 70 mm
- 3) Heavily calcified annulus or leaflets
- 4) Significant CAD requiring revascularization
- 5) Active bacterial endocarditis
- 6) Any percutaneous coronary, carotid, endovascular intervention or carotid surgery within 30 days or any coronary or endovascular surgery within 3 months
- 7) Renal insufficiency requiring dialysis
- 8) Life expectancy of less than twelve months
- 9) Subject is participating in concomitant research studies of investigational products that have not reached their primary endpoint
- 10) Pulmonary hypertension ≥ 70 mmHg at rest
- 11) Mitral valve anatomy which may preclude proper device treatment
- 12) Right-sided congestive heart failure with echocardiographic evidence of severe right ventricular dysfunction and/or severe tricuspid regurgitation
- 13) Severe liver disease
- 14) Patient is pregnant or lactating
- 15) Hypersensitivity to Nickel or Chromium
- 16) Clinically significant bleeding diathesis or coagulopathy

	REPAIR - Transcatheter REPAIR of Mitral Insufficiency with Cardioband System Post Market Study Protocol ID CB1-3	
---	---	---

- 17) History of mitral valve repair
- 18) TIA or CVA within the past 3 months
- 19) Subjects in whom transesophageal echocardiography is contraindicated
- 20) Patients who cannot tolerate anticoagulation/antiplatelet regimen
- 21) Patients with known severe reaction to contrast agents that cannot be adequately premedicated

4. Data collection

Patients will be recruited from the pool of patients who are referred for transcatheter mitral valve repair.

4.1. Key Pre-Implantation Procedures:

- 1. History and Physical
 - 2. TTE , TEE and/or CT
 - 3. 6 minute walk test
 - 4. KCCQ
- 

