5. STUDY VISITS AND PROCEDURES

The study will commence following institutional medical ethics committee

Screening of patients will be performed according to the hospital standard screening for transcatheter mitral valve repair and replacement. Patients will give a written consent for health information release prior to screening process. The treatment procedure will be performed according to the instructions outlined in the current approved IFU. The clinical assessments will be done as per routine practice at the participating sites.

Data will be collected at the following time points (as expected in the course of a normal treatment): baseline, procedure, discharge, clinical follow-up at 30 days, 6 months, 12 months, and 24 months from the index procedure. Data from any other additional time points may be collected and analyzed if available.

	REPAIR - Transcatheter REPair of Mitral Insufficiency with CaRdioband System Post Market Study Protocol ID CB1-3	
---	---	---

The procedures associated with each study visit are outlined and summarized in Table 1.

[figure not shown]

Table 1. Variables captured in the REPAIR database at various time points.

Procedure	Screening	Baseline	Implantation	Discharge	30 days	6 months	12 months	24 months
Visit Number	-1	1	2	3	4	5	6	8
Range	-1 month	-1 month	0	NA	-1 wk/+ 2 wks	+/- 1 month	+/- 1 month	+/- 1 month
Data release Consent	X							
Study informed consent		X						
Demographics		X						
Wearable data watch		X	X	X	X	X	X	X
Medical History		X						
Routine Blood tests		X		X	X	X	X	X
General Clinical State		X		X	X	X	X	X
Adverse Events		X	X	X	X	X	X	X
Medication Profile		X		X	X	X	X	X
Mitral Regurgitation Assessment by TTE	X	X		X	X	X	X	X
Mitral Regurgitation Assessment by TEE		X	X					
Mitral valve anatomy (by Echo and/or CT)	X							
Coronary Angiography (within the past 12 months, optional)	X							
6-minute walk test		X			X	X	X	X
QoL questionnaire (KCCQ)		X			X	X	X	X
NYHA Functional Class		X			X	X	X	X
Cardioband Implantation			X					

	REPAIR - Transcatheter REPAIR of Mitral Insufficiency with Cardioband System Post Market Study Protocol ID CB1-3	
---	---	---

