5.2. Unscheduled Visits

An unscheduled visit will be any visit to the clinical site other than the specific visits requested in the protocol. The Investigator or trained and qualified staff will perform all procedures necessary to evaluate the study participant at these visits, and record the visit in the subject's chart. The Principal Investigator must be notified by the subject immediately of any unscheduled visits to any medical facilities during the study period. (Subjects will be instructed to report).

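### Can disabling stroke in the 30-day safety composite be graded when the visit schedule lists no mRS?

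*Combined protocol and SAP*

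**What the plan says.** The composite is secondary endpoint 10 in the synopsis and item 12 in section 3.2.3. It is freedom from death and "major adverse events defined as disabling stroke, myocardial infarction (peri-procedural or spontaneous), renal failure requiring dialysis", along with bleeding, tamponade and device-related surgery components. It is assessed "at 30 days from the implant procedure or hospital discharge, whichever is later", and each component is also to be evaluated singly.

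Appendix 2 (Neurologic events) grades severity with two scores. The disabling class is "Disabling stroke: an mRS score ≥ 2 at 90 days plus an increase in ≥ 1 mRS category from the pre-stroke baseline". The complement is "Non-disabling stroke: an mRS score ,2 at 90 days or without an increase ≥ 1 mRS category from the pre-stroke baseline" (the comma before the 2 is a lost less-than sign). The same entry classes a stroke as "Periprocedural if it occurs within 30 days of the intervention, or if beyond 30 days in the patient not yet discharged".

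The schedule in section 5 is headed "Table 1. Variables captured in the REPAIR database at various time points". Its rows include the 6-minute walk, KCCQ, NYHA class and adverse events, but no mRS at baseline or later. The follow-up visits are at 30 days and at 6, 12 and 24 months. In the visible text, mRS appears only in the stroke severity definition.

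**The concern.** A component of a safety endpoint is defined by two measurements, and the table of captured variables contains neither. No visit falls near the day when the 90-day score is due, so routine follow-up would not supply it by chance.

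The pre-stroke score cannot simply be set to zero. The only exclusion for previous cerebrovascular events is "TIA or CVA within the past 3 months", so a subject with an older stroke and residual disability can enrol.

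If a score were missing, a non-fatal stroke might be neither disabling nor non-disabling. The visible text has no rule for counting it, so the choice would be made after the event was known. In a single-arm study of about 50 subjects with safety as one of its two objectives, that deserves a check.

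**Working it through.** The plan states no figure on this point, so there is none to reproduce. The check has four parts.

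**1. Does any scheduled visit supply the 90-day score?** The windows come from the range row of Table 1, with a month taken as 30.44 days.

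- 30-day visit, minus 1 week to plus 2 weeks: 30 − 7 = day 23 to 30 + 14 = day 44.
- 6-month visit, plus or minus 1 month: 5 × 30.44 = day 152.2 to 7 × 30.44 = day 213.1.
- Stroke on days 0 to 30: score due on days 0 + 90 = 90 to 30 + 90 = 120.
- Gap after the 30-day window: at least 90 − 44 = 46 days.
- Gap before the 6-month window: 152.2 − 120 = 32.2 days (day-30 stroke) to 152.2 − 90 = 62.2 days (day-0 stroke).
- Stroke days whose 90-day point falls inside the 6-month window: 152.2 − 90 = 62.2 to 213.1 − 90 = 123.1. Within the composite, these can arise only in a subject still in the index hospitalization.

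No scheduled visit supplies the score. That is expected of a measurement timed from an event and not from the implant.

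**2. Which strokes need which score?**

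| 90-day mRS | Pre-stroke mRS | Class |
|---|---|---|
| below 2 | known or not | non-disabling |
| 2 or more | known | graded by the rise |
| 2 or more | missing | cannot be graded |
| missing | known or not | cannot be graded |

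Only the last two rows are a problem. A stroke that is fatal within the window counts through all-cause mortality, and some intracranial bleeds count as life-threatening bleeding. The exposure is the remaining non-fatal strokes.

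**3. Is absence from Table 1 evidence that the score is not collected?** Compare other Appendix 2 definitions with the table. Periprocedural infarction needs ECG changes, stroke classification uses neuroimaging, bleeding grades use units transfused, and kidney injury uses urine output. None has its own row, so Table 1 does not list event-triggered data. The other provisions are these:

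- The opening of Appendix 2 directs that events be reviewed and reported under its definitions. Reporting a stroke that way requires its mRS.
- Section 7.1 requires follow-up of every event until it is resolved or explained.
- The close of Appendix 2 calls for independent adjudication of neurological events.
- Section 5 permits data from extra time points.
- At an unscheduled visit (section 5.2), staff "will perform all procedures necessary to evaluate the study participant at these visits".
- The contents list puts section 9.1.2, on adverse event reporting, at page 32 and Appendix 2 at page 35. The text of 9.1.2 is not visible in the public copy.

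**4. How large could the effect be?**

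- One event in 50 subjects: 100 / 50 = 2.0 percentage points.
- Exact 95% limits: 0/50 gives 0% (0 to 7.1%) and 1/50 gives 2% (0.05 to 10.6%). The intervals overlap almost entirely.
- The documents give no stroke rate. Assuming 1%, 2% or 4%, the chance of at least one stroke, 1 − (1 − p)^50, is 39.5%, 63.6% or 87.0%. A stroke is therefore quite possible, but it matters here only if it is non-fatal, not captured by another component and left without a needed score.

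**The case for a change.** The best argument for a change is that none of these provisions names mRS or a day. Follow-up until resolution sets no scale. Extra time points are optional. The committee's visible remit in section 7.2 is the relation of events to device or procedure, not severity. Assessments follow routine practice at up to 20 sites, so nothing visible guarantees a uniform score. A disabling-stroke rate must be produced because components are reported singly. A prospective baseline score can be had only before implantation, and it would cost little.

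Part of this stands: the visible text does not say where either score is recorded, and naming the place would be tidy. The rest is weaker. The definition asks for the pre-stroke state, which can be taken from history after the event, so scoring every subject at enrolment is a preference. The sentence on the committee's remit is followed by text that cannot be seen, and Appendix 2 asks for adjudication of neurological events in general terms. The reporting section that would most naturally hold the rule is also unseen, and its absence from the public copy cannot be held against the plan.

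**Conclusion.** No change is called for. The definitions and windows are as described, but the step from an item not listed in the visit table to an endpoint that cannot be evaluated does not hold. A team that follows the Appendix 2 instruction would record the pre-stroke and 90-day scores when a stroke occurs, by telephone if need be, and finalise the composite once the score is in. This is missing detail of a kind that event forms and adjudication procedures ordinarily fill.

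There is no timing contradiction either: the 30-day or discharge limit is reasonably read as governing when the stroke happens, and the 90-day score as grading it afterwards.

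The residual effect is at most 2 percentage points per ungraded stroke at 50 subjects. It is zero if that stroke was truly non-disabling and counted as a non-event, and the ceiling falls if enrolment is expanded as section 6.1 allows. The endpoint is unpowered and has no performance goal, so no decision turns on it. The conclusion assumes that the Appendix 2 instruction is followed and that nothing in the unseen text contradicts it.
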